## 16.2. Local Tolerability Assessments

The evaluator will assess local application site tolerability by rating the itching and burning/stinging at the Baseline visit and site visits at Weeks 2, 4, 8 and 12 (End of Study) or unscheduled visits. The evaluator will determine the score for each of these variables by asking the patient to grade their experience over the **past 24 hours**. The definitions of grades provided in [Table 5](#) will be applied to these evaluations. The Local Tolerability Assessment evaluations of itching and burning/stinging will be made by the investigator at the time of the visit.

**Table 5: Local Tolerability Assessment Scale**

Grade	Description
Itching	
0 – None	No itching
1 – Mild	Slight itching, not really bothersome
2 – Moderate	Definite itching that is somewhat bothersome
3 – Severe	Intense itching that may interrupt daily activities and/or sleep
Burning/Stinging	
0 – None	No burning/stinging
1 – Mild	Slight burning/stinging sensation; not really bothersome
2 – Moderate	Definite warm, burning/stinging sensation that is somewhat bothersome
3 – Severe	Hot burning sensation that causes definite discomfort and may interrupt daily activities or sleep

Application site reactions (itching and burning/stinging) are not to be recorded as adverse events unless they result in either:

- The temporary discontinuation of the study product.
- The discontinuation of the patient from the study.
- The use of a new concomitant medication in order to treat this event.

Any other application site reaction not listed above should be recorded as adverse events in the source document and eCRFs.

## 17. ADVERSE EVENTS

### 17.1. Departure from the Protocol for Individual Patients

When an emergency occurs requiring a departure from the protocol for a patient, departure will be only for that patient. In such circumstances, the investigator or other physician in attendance will contact the Medical Monitor or the Sponsor by telephone and follow up with a written description as soon as possible. The overseeing IRB should also be notified.

### 17.2. Definitions

An adverse event (AE) is defined as any untoward medical occurrence in a patient administered a medicinal product and which does not necessarily have to have a causal relationship with this treatment. An adverse event can therefore be any unfavorable and unintended sign, symptom, or disease temporally associated with the use of a medicinal product, whether or not considered related to this medicinal product.

A serious adverse event (SAE) is an adverse event that results in any of the following outcomes:

- Death
- Life-threatening event (i.e., the patient was, in the opinion of the investigator, at immediate risk of death from the event as it occurred. It does not include an event that, had it occurred in a more severe form, might have caused death)
- Requires in-patient hospitalization or prolongs hospitalization
- A persistent or significant disability/incapacity or substantial disruption of the ability to conduct normal life functions
- Congenital anomaly/birth defect
- Other adverse events that may be considered serious based upon appropriate medical judgment, may jeopardize the patient and may require medical or surgical intervention to prevent one of the outcomes listed above.

Immediately Reportable Adverse Events (IRAE) is any serious AE or any AE that necessitates discontinuation of study product, including pregnancy.

Unexpected Adverse Event is any adverse drug experience, the specificity or severity of which is not consistent with the current approved product labeling (package insert) for the study product, the Investigator's Brochure, or as described in the clinical protocol and consent materials.

Intensity of Adverse Events are the maximum intensity of an AE during a day should be recorded on the eCRF. If the intensity of an AE changes over a number of days, then separate entries should be made having distinct onset dates for the changes in severity.

- Mild - AEs are usually transient, requiring no special treatment, and do not interfere with patient's daily activities.
- Moderate - AEs typically introduce a low level of inconvenience or concern to the patient and may interfere with daily activities, but are usually ameliorated by simple therapeutic measures.
- Severe - AEs interrupt a patient's usual daily activity and traditionally require systemic drug therapy or other treatment.

### 17.3. Causal Relationship to Study product

The following criteria should be used in assessing the apparent causal relationship of an AE to study product:

Definitely - The AE:

- follows a reasonable temporal sequence from study product administration
- abates upon discontinuation of the study product (de-challenge)
- is confirmed by reappearance of the reaction on repeat exposure

Probably - The AE:

- follows a reasonable temporal sequence from study product administration
- abates upon discontinuation of the study product (de-challenge).
- cannot be reasonably explained by the known characteristics of the patient's state.

Possible - The AE:

- follows a reasonable temporal sequence from study product administration
- but that could readily be produced by a number of other factors.

Unlikely - The AE:

- follows a reasonable temporal sequence from study product administration.
- could have been produced by either the patient's clinical state or by study product administration.

Not related - The AE:

- does not have a reasonable temporal association with the administration of study product
- has some other obvious explanation for the event.

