#### 17.7. SAE & AEs Requiring Discontinuation of Study Drug, including Pregnancies

ANY SAE, WHICH OCCURS AFTER A PATIENT HAS ENTERED THE STUDY, WHETHER OR NOT RELATED TO STUDY PRODUCT, MUST BE REPORTED TO THE SPONSOR OR ITS DESIGNEE IMMEDIATELY (WITHIN 24 HOURS) VIA TELEPHONE, EMAIL OR FACSIMILE. IF INITIALLY REPORTED VIA TELEPHONE, THIS MUST BE FOLLOWED-UP BY A FACSIMILE OR EMAIL OF THE WRITTEN SAE REPORT WITHIN 24 HOURS OF THE CALL TO THE SPONSOR OR ITS DESIGNEE.

Non-serious events that require discontinuation of study product (including laboratory abnormalities) should be reported to the Sponsor or its designee immediately and within 1 working day.

Patients who discontinue due to experiencing study product-related adverse events should be followed clinically until their health has returned to baseline status, or until all parameters have returned to normal. It is expected that the investigator will provide or arrange appropriate supportive care for the patient.

A patient who experiences a severe adverse event related to study product will be discontinued from the study, but, regardless of the duration of the study, patients that exhibit serious adverse event (SAE), will be followed up until the SAE resolves, based on investigator's medical judgment or are considered to be chronic (stabilized for at least 30 days). For safety reporting instructions see SAE and Pregnancy Form Report Instructions.

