8.1.5 Handling of Dropouts or Missing Data

Missing data for the ITT population will be estimated by multiple imputation and subsequently analyzed. Missing lesion count and IGA data will be derived for the analysis using the method of Markov Chain Monte Carlo (MCMC) multiple imputation. The pattern of missing observations in each treatment group cannot influence the missing value estimation in the other group because the imputation will be conducted independently for each treatment group.

Last observation carried forward (LOCF) will be used to impute missing data for the efficacy analyses using the PP population.

Patients that discontinue from the study due to an AE related to study treatment or documented lack of treatment effect will be included in the PP population. Data for these subjects will not be imputed by multiple imputation or LOCF but rather their data will be imputed with values consistent with their status as treatment failures. For these subjects, values for lesion count and IGA will be imputed such that change from Baseline is zero, meaning the values will be set to the Baseline value. This imputation will be done after the data for all subjects has been through the MI process.

Incomplete start and end dates for medications will be imputed. Other safety data will not be imputed and will be summarized on an observed case basis.

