8.8.2 Adverse Events (AEs)

All AEs occurring during the study will be recorded and classified on the basis of MedDRA terminology. Descriptions of AEs will include the date of onset, the date the AE ended, the severity of the AE, the relationship to study product, the action taken regarding study product usage, the action taken to treat the AE, and the outcome. All reported treatment-emergent AEs (TEAEs) will be summarized by the number of patients reporting AEs, system organ class, severity, seriousness, and relationship to study product. TEAEs are those AEs with an onset on or after the date of the first study product application; if the AE is not indicated as prior to first application on the CRF then it will be considered a TEAE.

AEs will be summarized by treatment group and severity. Each patient will be counted only once within a system organ class or a preferred term by using the AEs with the highest severity within each category.

AEs will be summarized by treatment group and relationship to study product. Each patient will be counted only once within a system organ class or a preferred term by using the AEs with the greatest relationship within each category.

If relationship to study drug is reported as definitely, probably, or possible, then this is defined as related. If relationship to study drug is reported as unlikely or not related, then this is defined as unrelated.

Comparisons among treatment groups will be made by tabulating the frequency of patients with one or more AEs (classified into MedDRA terms) during the study. The Fisher's Exact test will be used to compare the proportion of patients in each treatment group who report any AE at a

significance level of 0.05. The specific system organ classes and preferred terms analyzed will be those that are reported by at least one percent of the patients in any treatment group.

All information pertaining to AEs noted during the study will be listed by patient, detailing verbatim given by the investigator, preferred term, system organ class, start date, stop date, severity, actions taken, and drug relatedness. The AE onset will also be shown relative (in number of days) to the day of initial application of the randomized study product.

Serious adverse events (SAEs) will be tabulated by patient within treatment groups.

In addition, a list of patients who discontinued from the study and a list of patients who experienced SAEs will also be provided.

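### Protocol 17.3 words 'Unlikely' so that it overlaps with 'Possible' and names the product as a candidate cause, yet SAP 8.8.2 tabulates every 'Unlikely' event as not related

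*Protocol*

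**What the plan says.** Protocol 17.3 lists the criteria that investigators should use for five levels: Definitely, Probably, Possible, Unlikely and Not related. 'Unlikely' has two criteria. The event "follows a reasonable temporal sequence from study product administration", and it "could have been produced by either the patient's clinical state or by study product administration". 'Possible' shares the first criterion and continues "but that could readily be produced by a number of other factors". 'Not related' is an event that "does not have a reasonable temporal association with the administration of study product" and that has some other obvious explanation.

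SAP 8.8.2 reduces the five levels to two. On one side: "If relationship to study drug is reported as definitely, probably, or possible, then this is defined as related". On the other: "If relationship to study drug is reported as unlikely or not related, then this is defined as unrelated". The shells for the TEAE and serious TEAE characteristics tables (14.3.1.2.1, 14.3.1.3.1) and relationship tables (14.3.1.2.4, 14.3.1.3.4) show only Related and Not Related and repeat the rule in their footnotes. Protocol 19.6 plans a summary by relationship without stating this reduction, and SAP Section 10 does not list it among the changes to the planned analyses.

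The word 'related' is also used in SAP 8.1.5, in a rule that begins "Patients that discontinue from the study due to an AE related to study treatment". These patients, together with those who leave for documented lack of effect, stay in the per-protocol population and have their values set to baseline as treatment failures. SAP 8.4.4 repeats the rule. Neither section says which causality levels count.

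**The concern.** A related/unrelated table is only as good as the line between the two groups. Here the line falls between two levels that the protocol does not separate. The level placed on the unrelated side is the one whose definition expressly names the product as a candidate cause.

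At stake is what a reader takes from the related-event summaries. Someone who reads Not Related would assume that the investigator had all but excluded the product. Under the written criteria the investigator may have judged only that the disease and the product were both credible explanations. In rosacea that judgement is plausible for some events: burning and itching are scored as disease symptoms in the PAPSS (Protocol 14.5), and Protocol Section 7 also describes them as known effects of benzoyl peroxide.

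**Working it through.** No arithmetic applies. The check sets the definitions beside the grouping (criteria paraphrased from Protocol 17.3, grouping from SAP 8.8.2):

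| Level | Timing fits product use? | Further criteria | Tabulated as |
|---|---|---|---|
| Definitely | Yes | Resolves on stopping and recurs on re-exposure | Related |
| Probably | Yes | Resolves on stopping; not reasonably explained by the patient's condition | Related |
| Possible | Yes | Other factors could readily explain it | Related |
| Unlikely | Yes | Patient's condition or the product could explain it | Not Related |
| Not related | No | Another obvious explanation | Not Related |

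1. **Do 'Possible' and 'Unlikely' overlap?** Take application-site pain, which Protocol 16.1 says is recorded as an adverse event, on day 10 in a patient with active rosacea (an invented case). The timing fits. The disease is another factor that could readily explain it, so 'Possible' is met. The disease or the product could explain it, so 'Unlikely' is met. Both grades are correct as written.

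2. **Does the choice matter?** Yes. The first grade is tabulated as Related and the second as Not Related. No other adjacent pair of levels straddles the SAP's cut.

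3. **Do the upper levels take such events?** Often not. 'Definitely' needs re-exposure. 'Probably' fails when the patient's own condition is a reasonable explanation, even if the event resolved on stopping. The site is then left with 'Possible' or 'Unlikely'.

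4. **What else falls into 'Unlikely'?** If both 'Not related' criteria must hold, as the list format suggests, an event with coincident timing but a clear other cause cannot be 'Not related'. 'Unlikely' then mixes such events with events the product may well have caused, and the two-level table cannot separate them.

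5. **How large is the effect?** Neither document gives adverse event rates for this trial or a distribution of causality grades, so the number of events affected cannot be derived. One thing follows by logic: a count of patients with a related event that includes 'Unlikely' can only equal or exceed the count the SAP will report.

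**The case against.** The strongest reply is that the effect is confined to secondary tables. The Fisher's exact comparison of TEAEs by arm (Protocol 19.6, SAP 8.8.2, Table 14.3.1.2.2) ignores causality, so in a blinded vehicle-controlled trial it is untouched by grading. Sites report every SAE regardless of relationship (Protocol 17.7). Dryness, scaling, itching and burning/stinging become adverse events only if they lead to interruption of product, withdrawal or new medication (Protocol 16.1, 16.2). Otherwise they are scored and tabulated by arm without attribution. The listings also carry a relationship field for each event, though the shells do not show whether it has five levels or two. And grouping 'Unlikely' with unrelated would be coherent if the word meant improbable causation, which is how many investigators may read the label. All of this stands. It limits the consequence but does not remove the conflict, because the written 'Unlikely' criteria do not say improbable.

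Three stronger readings are tempting, and the documents do not support them.

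- A reader might infer that the two levels are in effect reversed, since only 'Unlikely' names the product. But the section concerns relationship to the product, and the reference to other factors under 'Possible' presupposes the product as a candidate. The text shows overlap, with no known direction of misgrading.
- A reader might infer that 'Unlikely' events escape the operational rules on relatedness, such as "A patient who experiences a severe adverse event related to study product will be discontinued from the study", the follow-up rules in 17.4 and 17.5, or expedited reporting in 17.6. SAP 8.8.2 is a tabulation rule, and nothing applies it to those sections. They use the word 'related' without saying whether 'Unlikely' counts.
- A reader might infer that this is the typical event in the trial. The filter on local reactions in Protocol 16.1 and 16.2 argues against that.

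**Conclusion.** The concern holds for the related-event summaries. An event that meets the protocol's written criteria for 'Unlikely' is always tabulated as Not Related, although those criteria name the product as a possible cause, and the same event could equally have been graded 'Possible' and tabulated as Related. This affects the four table shells named above. It rests on the wording alone and assumes that investigators apply the criteria as written. If they grade by the label, fewer events are affected. The size is unknown.

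A second effect is possible but not established. SAP 8.8.2 holds the SAP's only definition of 'related'. If it also governs SAP 8.1.5 and 8.4.4, a patient who leaves because of an event graded 'Unlikely' would not be treated as a failure under that rule and, without a Week 12 visit, would fall outside the per-protocol population. The documents do not say whether it does.

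**What to change.** Before unblinding:

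- **SAP 8.8.2 and shells.** Show all five causality levels in Tables 14.3.1.2.4 and 14.3.1.3.4, or add a row for related including 'Unlikely' as a sensitivity summary. This works with grades already given.
- **SAP 8.1.5 and 8.4.4.** State which causality levels make a discontinuation related to study treatment.
- **Protocol 17.3 and SAP 8.8.2.** Reconcile the wording of 'Possible', 'Unlikely' and 'Not related' with the grouping. Relatedness also enters the discontinuation provision in Protocol 17.7, so the sponsor must settle which wording is intended, and no definition is proposed here.

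The SAP changes cost one extra table split and a sentence or two, with a possibly higher reported related-event rate. A protocol wording change costs more: amendments need IRB approval (Protocol 20.2), and events graded under different definitions would not be directly comparable. That is a reason to make the table change in any case.

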### 17.4. Eliciting and Reporting of Adverse Events

The investigator will periodically assess patients for the occurrence of adverse events. In order to avoid bias in eliciting adverse events, the patient or parent/legally authorized representative should be asked a non-specific question (e.g., "How have you been feeling since your last visit?") to assess whether any AE has been experienced since the last visit. All adverse events (as defined in [Section 17.2](#)), either observed by the Investigator or one of his/her medical collaborators, or reported by the patient spontaneously, or in response to direct questioning, will be reported and documented in the source and the study reporting forms. When reporting an adverse event, the Investigator must assign a severity grade to each event and declare an opinion on the relatedness of the event to the study product or procedure. Serious or unexpected adverse events must be reported to the CRO within 24 hours of when the Investigator first learns of the occurrence of the event.

Adverse events will be documented in the source document and recorded in a timely manner on case report forms. Adverse events that are identified at the last assessment visit (or the Early Termination Visit) must be recorded on the AE eCRF with the status of the AE noted.

Adverse event reporting begins from the signing of informed consent/assent. Study product-related adverse events should be followed until resolved or 30 days after the final study treatment. Regardless the duration of the study, patients that exhibit serious adverse event (SAE), will be followed up until the SAE resolves, based on investigator's medical judgment or are considered to be chronic (stabilized for at least 30 days). All events that are ongoing at this time will be recorded as ongoing on the eCRF.

#### 17.5. Expedited Reporting Responsibilities of the Study Center

For any serious or unexpected adverse event, the Sponsor or its designee must be notified within 24 hours of when the Investigator first learns of the occurrence of the event. Expedited reporting requirements for serious adverse events are described below. Adequate information must be collected with supporting documentation to complete a standard report for submission to Sol-Gel. The adverse event term on the AE eCRF and the SAE report should agree exactly. Special attention should be given to recording hospitalizations and concomitant medications.

Patients with unresolved study or product-related adverse event(s) or serious adverse event(s) should be followed by the investigator until the events are resolved, events determined to be chronic or the patient is lost to follow-up. Resolution means the patient has returned to the Baseline state of health, or the investigator does not expect any further improvement or worsening of the adverse event. The investigator should continue to report any significant follow-up information to the sponsor up to the point that the event has resolved. Any serious adverse event reported by the patient to the investigator that occurs within 30 days after the last assessment, and are determined by the investigator to be reasonably associated with the use of the study product, should be reported to the sponsor within 24 hours of when the Investigator first learns of the occurrence of the event.

When reporting a serious adverse event (SAE) the Investigator (or the Study Coordinator) will promptly report any serious adverse event or pregnancy to the Sponsor or its designee by telephone email, immediately after the investigator becomes aware of the event. An SAE form should be completed and sent by fax, email, or overnight courier to the Sponsor or its designee within 24 hours of knowledge of the event by the site. In many cases, only preliminary information will be available. Appropriate follow up information should be sought (hospital discharge summaries, operative reports etc.) and a follow up SAE report form submitted. A designation of causality from the study product should always be included with a follow up report. Assess and report the causality of the event.

#### 17.6. Submitting an Expedited Safety Report to the IRB

Once all supporting documentation is received for the reported event, the Medical Monitor, in conjunction with Sol-Gel, will determine if the safety report is eligible for expedited review. When expedited safety reporting to regulatory authorities is indeed required, the Investigator should review and update any newly available materials at once. Follow-up queries may be sent to the study center to further clarify the event.

The Sponsor, or its designee, is responsible for submitting reports of serious, unexpected related AEs to regulatory authorities on an expedited basis, according to the ICH E2A Guideline and to other regulatory authorities according to national and local regulations as required. The Sponsor, or its designee, is responsible for prompt submission to the IRB or EC of any expedited SAE reports submitted to regulatory authorities. All investigators participating in ongoing clinical studies will receive copies of the SAE reports submitted on an expedited basis to regulatory authorities

